#### Version 1.0

|   |              | Wk 1  | TV1    |              | 2 TV2 |              | 3 TV3 | Wk 4         | Wk 5 [C]                    |
|---|--------------|-------|--------|--------------|-------|--------------|-------|--------------|-----------------------------|
| Visit                                       | SV1          | Pre** | Post   | VVK 2        | 2172  | VVKC         | 5173  | TV4          | EOS 1                       |
|   |              | Rand  | Rand   |              |       |              |       |              |                             |
| Weeks from
Treatment Date                | 0            | (     | )      | 1            | 1.5   | 2            | 2.5   | 3            | 4                           |
| Assurance of effective                      | Ŭ            | `     |        |              |       |              |       |              |                             |
| birth control (females of                   |              |       |        |              |       |              |       |              |                             |
| childbearing                                | Х            |       |        |              |       |              |       |              |                             |
| potential)
Pain assessment               | X            | Х     |        | x            | x     | x            | x     | x            | Х                           |
| Monofilament                                |              |       |        |              |       |              |       |              |                             |
| Test (10-point)                             | Х            | Х     |        | Х            | X     | X            | X     | Х            | Х                           |
| Serum Creatinine                            | Х            |       |        |              |       |              | cor   | 6            |                             |
| Blood Glucose                               | Х            | Х     |        | Х            | Х     | X            | X     | Х            | X                           |
| HbA1c Lab                                   | Х            |       |        |              |       |              | 6     |              | Х                           |
| Take X-ray to rule                          |              |       |        |              |       | aran L       |       |              |                             |

\*\*Pre-randomization assessments are only performed if treatment is not done on the same day as screening. Otherwise, Screening and Randomization (first treatment) can occur on the same day, screening procedures are performed, then followed by randomization and completion of post randomization schema of events.

| Version 1.0 | Date: June 7, 2024 |
|-------------|--------------------|
|             |                    |

#### 4.5.2 Screening Phase

The subject will sign and date the ICF and HIPAA authorization (according to site practices) prior to collection of any protected health information, as well as any study-related procedures. A subject ID will be assigned to each subject in successive order of entering the study after signing the ICF, beginning with 001 at each site.

SV1 can occur up to 2 days prior to randomization. However, subjects who meet all eligibility criteria can enter the Treatment Phase immediately once all of the eligibility criteria are reviewed and the subject meets all inclusion and no exclusion criteria.

#### 4.5.3 SV1: Procedures to be performed include:

- Informed consent will be obtained prior to the collection of any protected health information as well as any study related procedures and the subject will sign a written ICF
- Assess current wound therapies for prohibited therapies within 30 days of randomization
- Demographics
- Medical history
- Physical examination
- Assess concomitant medications
- Vital signs
- Pain assessment (see section 8.5)
- Labs: HbA1c (if no documented results within 90 Days of the first screening visit are available), assess blood glucose, and serum creatinine (if no documented results within 6 months of the first screening visit are available)
- Pregnancy test (blood or urine) if female subject is of childbearing potential. If female is
  not of childbearing potential the reason for inclusion must be included in the study record
- Assurance of effective birth control if female subject is of childbearing potential
- Ulcer history
- Target Ulcer assessment
- Assess signs and symptoms for clinical infection of the target ulcer (see section 8.6.3)
- Target ulcer foot neuropathy Semmes Weinstein 10-point test; (see section 8.9)
- Clean the target ulcer
- Debridement of the target ulcer, if applicable (see Appendix E)
- Digital imaging of the target ulcer
- Record target ulcer measurements
- Obtain X-ray to rule out osteomyelitis or bone infection of the affected foot
- ABI, SPP, TCOM, TBI, PVR measurement or Arterial Doppler Study will be obtained (see Appendices B-D)
- Initiate offloading of the target ulcer

| Version 1.0 | Date: June 7, 2024 |
|-------------|--------------------|
|-------------|--------------------|

- Assessment of subject's eligibility to continue in the study
- Apply appropriate SOC to target ulcer and outer dressing if patient does not enter into the treatment phase immediately following SV1

#### 4.5.4 Treatment Phase

When determining the visit dates, the reference should always be seven days (±2 days). Every attempt should be made to maintain subjects on their original treatment schedule.

#### 4.5.4.1 TV1: Pre-Randomization

The Treatment Phase begins with a series of assessments designed to confirm the subject's continued eligibility (Pre-randomization, Table 1). The following assessments and activities are performed at this visit (unless randomization is performed at the same visit as screening):

- Medical history changes from previous visit
- Physical examination changes from previous visit
- Assess concomitant medications, changes from previous visit and prohibited therapies
- Vital Signs
- Pain assessment (see section 8.5)
- Assess blood glucose
- Target ulcer Assessments
- Assess signs and symptoms for clinical infection of the target ulcer (see section 8.6.3)
- Target ulcer foot neuropathy Semmes Weinstein 10-point test; (see section 8.9)
- Clean the target ulcer
- Debridement of the target ulcer if applicable (see Appendix E)
- Digital imaging of the target ulcer
- Record target ulcer measurements
- Assessment of offloading
- Target ulcer closure assessment will be determined by a site Investigator
  - If the subject is seen on a subsequent visit to enter the treatment phase and the target ulcer is 100% re-epithelialized, the subject will be considered a screen failure.
- Assessment of subject's eligibility to continue in the study
- If the subject is eligible, they will enter the treatment phase
- If the subject is not eligible, discharge the subject from the study as a screen failure

#### 4.5.4.2 TV1: Randomization

The following assessments and activities are performed at this visit:

- Randomize the subject
- Apply appropriate treatment to target ulcer:
  - Apply SOC therapy with Helicoll® Group 1
  - Apply SOC therapy with Epifix® or Grafix® Group 2
- Apply outer layer dressings, including first layer non-adherent and porous, second layer absorbent 4x4 gauze pads & third layer - soft roll and compressive wrap (Dynaflex™ or equivalent).
- Check for any changes in the subject's health and assess them for any adverse effects and adverse events
- Ensure offloading of the wound is satisfactory
- Schedule the next study visit for one week later (±2 days), except TV2 and TV3 where the patient will be seen twice weekly.

#### 4.5.4.3 Treatment Phase Visits: Weeks 2-4

The following assessments and activities are performed at these visits:

- Medical history changes from previous visit
- Physical examination changes from previous visit
- Assess concomitant medications, changes from previous visit and prohibited therapies
- ABI, SPP, TCOM, TBI, PVR measurement or Arterial Doppler Study will be obtained (see Appendices B-D)
- Vital Signs
- Pain assessment (see section & 5)
- Assess blood glucose
- Assessment of offloading
- Target ulcer foot neuropathy Semmes Weinstein 10-point test; (see section 8.9)
- Check for any changes in the subject's health and assess them for any adverse effects and adverse events
- Target ulcer closure assessment will be determined by a site Investigator
  - If the target ulcer is 100% re-epithelialized, the subject will exit study at the conclusion of the visit (the visit will be considered EOS1). Please perform all applicable assessments and study procedures associated with EOS1.
- Target ulcer Assessments
- Check for signs of clinical infection. If a clinical diagnosis of infection has been made, then the subject can be treated with oral antibiotics, but topical antibiotics or antimicrobial dressings CANNOT be used on the target ulcer (see section 8.6.3)
- Clean the target ulcer

- Debridement of the target ulcer if applicable (see Appendix E)
- Digital imaging of the target ulcer
- Record target ulcer measurements
- Apply appropriate treatment to the index ulcer:
  - Apply SOC therapy with Helicoll® Group 1
  - Apply SOC therapy with Epifix® or Grafix® Group 2
- For the TV2 and TV3 additional visit where application of a new Helicoll® does not occur, the primary dressing will be lifted from the wound site along with the Helicoll® Advanced Skin Substitute or Epifix® or Grafix®. If the Helicoll® Advanced Skin Substitute is adherent to the wound, moisten gently with saline before attempting to remove. Cleaning of the target ulcer as noted above is suggested, however debridement should be limited, and it is suggested that only a very gentle removal of any slough be performed at the investigator discretion. Digital Photography is then taken and the Helicoll® Advanced Skin Substitute or Epifix® or Grafix® and primary dressing should be placed back on the wound. If the primary dressing is soiled or damaged a new primary dressing can be applied. Additional assessments will be performed as referenced in the Schedule of Visits (Section 4.5, Table 1).
- Ensure offloading of the Target ulcer is satisfactory?
- Apply outer layer dressings, including first layers non-adherent and porous, second layer absorbent 4x4 gauze pads & third layer - soft foll and compressive wrap (Dynaflex™ or equivalent).
- The next visit will be scheduled for one week (+/- 2 days)

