#### 4.3 Subject Treatment Assessments

#### 4.3.1 DFU Assessments

During the Treatment Phase, subjects will be evaluated on a weekly basis, with the exception of week 2 and 3 where the patient will be seen twice weekly. Weekly/Twice-Weekly patient outcome evaluations include the Investigator's assessment of target ulcer healing and measurements of ulcer size using a ruler to measure wound area and provide photos of wounds, including photos of healed wounds.

Note: All procedures required during Screening are included in TV1 prior to the first treatment visit if the subject fulfills eligibility criteria.

Other evaluations during the Treatment Phase are detailed in the procedures section.

Subjects will be seen weekly (± 2 days) until the ulcer is healed or they meet protocol criteria to exit the study with the exception of the 2nd and 3rd week of treatment where the subject will be seen twice. For both groups, assigned treatment will be applied only once during the 2nd and 3rd week unless the investigator feels an additional application is necessary. If the additional application is not necessary, the additional visit will involve a dressing change and wound evaluation.

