#### 5 SUBJECT COMPLETION, SUCCESS/FAILURE, WITHDRAWAL AND SCREEN FAILURE

#### 5.1 Subject Completion

- A subject whose target ulcer has closed will be considered as having completed the study
- A subject who completes the Treatment Phase but still has an unhealed target ulcer will be considered as having completed the study
- A subject who does not complete the Treatment Phase and still has an unhealed target ulcer will be considered as not completing the study

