### 8.6.4 Investigator Assessment of Target Ulcer Closure

**"Complete healing**" of the target ulcer is defined as 100% re-epithelialization without drainage. At each visit, the Investigator will assess the ulcer by answering the following questions:

- Is target ulcer 100% re-epithelialized?
- Is drainage absent?

Both questions must be answered "yes" for the target ulcer to be considering having reached "complete closure."

**The date of complete healing** is defined as the date of the first assessment of 100% reepithelialization.

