The PP population will consist of randomized subjects with analysis conducted according to treatment received. The following subjects will be excluded: (a) subjects randomized but later found to be ineligible for the study because they failed to meet all inclusion and exclusion criteria; (b) subjects who did not complete the study; and (c) subjects with major protocol violations.

Safety Population

The safety population will be all subjects who were randomized and received at least one treatment.

Definitions

Baseline

For all parameters, baseline will be defined as the last available data point before the first treatment, which occurs at TV1.

Visit window data including study endpoints

For each weekly visit a window of ± 2 days will be adopted for data. If a specified time endpoint is outside of the window the last available visit data prior to the specified endpoint will be used.

Healing of Index Ulcer

Healing is defined as complete epithelialization of the ulcer without drainage observed in the index ulcer at two separate visits 2 weeks apart. If a subject fails this healing confirmation visit then they can continue in the trial with their assigned treatment provided that the index wound did not heal at the EOS visit.

Date of healing

The date of healing is defined as the date of the first assessment of index ulcer healing provided the index ulcer is still healed 2 weeks later.

Percentage area reduction from baseline

The percent change in the surface area of the Index Ulcer (PAR) will be calculated using the following formula:

((A1-A2)/A1)*100

Where A1 is the baseline area (at randomization), and A2 is the area at the specified time point.

Statistical Methodology

Missing data

Missing data may be the result of missed visits, subjects lost to follow-up or who have died, and may be endpoint data or covariate data.

The outcome of complete wound healing will be scored as **not** healed for the following events:

• The subject dies

- The subject has an amputation that affects the index ulcer
- The subjects is lost to follow-up
- The subjects is withdrawn from the trial
- The subject withdraws consent.

Missing PAR endpoint data within 5 weeks from TV1 will be not imputed.

Data QC

- 1. Inspect for accuracy of input:
 - 1.1. Plausible values
 - 1.2. Outliers or out-of-range values
- 2. Evaluate degree and distribution of missing data; for missing non-endpoint, out-of-range or non-plausible data, query PERI.

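### The protocol's exit sentence and healing date rest on re-epithelialization alone, while closure also requires absent drainage, so proportion closed and time to closure can disagree for the same subject

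*Protocol*

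**What the plan says.** Two protocol rules turn on epithelial cover alone.

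- **Exit (section 4.5.4.3, weeks 2-4):** "If the target ulcer is 100% re-epithelialized, the subject will exit study at the conclusion of the visit". The same bullet adds that "the visit will be considered EOS1", so it is the last study visit.
- **Date of complete healing (section 8.6.4):** the date "is defined as the date of the first assessment of 100% reepithelialization".

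Other rules require more.

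- **Complete healing and closure (section 8.6.4):** complete healing "of the target ulcer is defined as 100% re-epithelialization without drainage". The investigator answers one question on epithelialization and one on drainage, and closure needs yes to both.
- **Healing (SAP, Definitions):** "Healing is defined as complete epithelialization of the ulcer without drainage", seen at two visits 2 weeks apart. The SAP's date of healing is the first such assessment, provided the ulcer is still healed 2 weeks later.
- **Early exit elsewhere in the protocol:** section 4.3.1 keeps subjects in weekly follow-up "until the ulcer is healed or they meet protocol criteria to exit the study". Section 4.5 and footnote [C] of Table 1 bring the end-of-study visit forward when the wound heals.

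**The concern.** The event that ends observation is weaker than the event being counted. An ulcer can satisfy the exit sentence without satisfying the closure definition, and once the subject has left, nobody can record that drainage stopped. The protocol's healing date then uses the weaker event as well, so a subject not counted as closed may still have a time to closure.

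Both affected measures, the proportion closed and the time to closure, are secondary endpoints. They will be reported descriptively without hypothesis tests, so the reported proportions and times are themselves the result. The subjects affected would be those nearest to closure.

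**Working it through.** No sample size, power or event figure in the plan bears on this point, so there is nothing of that kind to reproduce. The check compares the rules and then applies simple arithmetic.

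**1. The rules side by side**

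| Rule | Place | Full epithelialization | Drainage absent | Second visit |
|---|---|---|---|---|
| Exit | Protocol 4.5.4.3 | required | not mentioned | no |
| Early end of study | Protocol 4.5; Table 1 footnote [C] | through 'heals' | through 'heals' | no |
| Closure | Protocol 8.6.4 | required | required | no |
| Date of complete healing | Protocol 8.6.4 | required | not mentioned | no |
| Healing and its date | SAP, Definitions | required | required | 2 weeks apart |

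**2. One subject followed through**

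Suppose an ulcer is fully epithelialised but still draining at the week 1 visit, and would be dry at week 2.

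- Exit under 4.5.4.3: yes, at day 7.
- Closure under 8.6.4: no, because drainage is present. No later visit can change that answer.
- Protocol date of complete healing, read literally: day 7. The two-question definition would give day 14, but that visit does not take place.
- Percentage of Healing (section 5.2 and Table 4; days to heal / 28 × 100): 7/28 = 25% on the literal date, against 14/28 = 50% on the two-question date.
- SAP healing: not met, and no SAP date of healing.
- PAR at that visit, if the area is recorded as 0: (A1 − 0)/A1 × 100 = 100% for any baseline area A1 in the eligible range of 1 to 10 cm².

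**3. Follow-up given up by exit**

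Table 1 places the post-baseline visits at weeks 1, 1.5, 2, 2.5, 3 and 4 from treatment. Exit at week 1, 1.5, 2, 2.5 or 3 leaves 5, 4, 3, 2 or 1 scheduled assessments unused. Exit at week 1 gives up 4 − 1 = 3 of the 4 weeks.

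**4. Weight of one subject**

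The plan is for 24 subjects, half to each group: 24/2 = 12 per arm. One subject is 1/12 = 8.3 percentage points of an arm's closure proportion, and two are 2/12 = 16.7.

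**5. Chance of meeting the state at all**

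The documents give no rate. For an assumed rate p, the chance of at least one such subject among 24 is 1 − (1 − p)^24:

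| Assumed p | At least one of 24 |
|---|---|
| 2% | 38% |
| 5% | 71% |
| 10% | 92% |

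**6. The SAP's second visit**

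A nominal visit exactly 2 weeks later exists in Table 1 only after week 1 (week 3) and week 2 (week 4). After weeks 1.5, 2.5, 3 and 4 there is none. If the subject exits at first epithelialization, no second visit takes place, whether the ulcer is dry or draining.

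**The case against.** **The wording has context.** The exit sentence is a sub-bullet of the closure assessment, which section 8.6.4 defines by two questions, so a site could take it as shorthand for closure. The date sentence concerns complete healing, defined just above it as free of drainage. Section 4.3.1 also leaves room for exit on other protocol criteria, so the clearest conflicts are with section 4.5 and footnote [C]. This stands in part: exit without closure is the literal reading, not a certain outcome. But two available readings across up to 5 sites are themselves the problem.

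**The SAP already dates healing correctly.** Its date requires drainage-free healing, and the protocol makes the SAP the detailed analysis document. This stands. The date defect lies in the protocol, and a reader should not infer that the SAP would give a draining ulcer a healing date.

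**The SAP's two-visit rule is the wider obstacle.** Under it, early exit prevents confirmed healing even for dry ulcers. This also stands. Aligning the exit sentence with the two closure questions would not by itself let an early-exit subject count as healed under the SAP. Conversely, solving the confirmation visit would not correct the protocol's date sentence.

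**Loss from the per-protocol population.** A reader might infer that such a subject becomes a non-completer and is then dropped from that population. Section 5.1 says: "A subject who does not complete the Treatment Phase and still has an unhealed target ulcer will be considered as not completing the study". But section 4.2 describes a Treatment Phase of up to 5 weeks and the exit visit counts as EOS1, so the subject can also be read as a completer. In any case the SAP analyses endpoints in the ITT population and specifies no per-protocol endpoint analysis.

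**Imbalance between arms.** The Helicoll instructions mention a gel that can be rinsed away, and a reader might infer more apparent drainage in that arm. Nothing in the documents equates the gel with drainage or shows a difference.

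**Photographic review.** Table 4 has the study chair determine closure from photographs. Absent drainage is listed as supporting data, but the documents do not say how it enters that review, so this is not an evident safeguard.

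**Conclusion.** The contradiction is real. The protocol ends participation and dates complete healing on one criterion, and defines closure on two. On the literal reading, an epithelialised but draining ulcer exits unclosed, cannot be recorded as closed later, and may still have a protocol healing date.

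The size is conditional. Each such subject is worth 8.3 percentage points of an arm's closure proportion, assuming 12 per arm. That is the weight of any one subject, not an estimate of bias, and the 2% to 10% range is illustrative. It would go too far to say that the secondary endpoints will be wrong: that requires at least one such subject and a site that follows the literal wording. The definition of PAR, the primary endpoint, is unaffected.

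This is an internal inconsistency that should be fixed. It touches descriptive secondary endpoints in a 24-subject convenience sample and does not undermine the primary analysis.

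**What to change.** 1. **Healing date.** In protocol section 8.6.4, define the date of complete healing as the first visit at which both closure questions are answered yes. This matches the closure definition in the same section and is purely an endpoint matter.
2. **Exit wording.** Reconcile section 4.5.4.3 with sections 4.3.1, 4.5 and 8.6.4, footnote [C] of Table 1, and the SAP's requirement of two visits 2 weeks apart, so that the exit event and the closure endpoint rest on one definition. The exit rule bears on when treatment stops, so the choice belongs to the sponsor and this review does not propose one.

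**Cost.** The first change is one sentence and needs no new data, because both questions are already asked at each visit. The second is a short protocol amendment with IRB approval, and a matching line in the SAP if its definition changes. Whether any subject attends further visits depends on the sponsor's choice. Up to week 4 from treatment those visits are already scheduled. If the SAP's two-visit rule is kept, Table 1 has no nominal visit 2 weeks after weeks 1.5, 2.5, 3 or 4, and the reconciliation must deal with that.
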